4. OBJECTIVES AND OUTCOME MEASURES

Objectives	Outcome Measures	Timepoint(s) of evaluation of this outcome measure (if applicable)
Primary Objective To demonstrate clinical non-inferiority, followed by superiority, of a shorter antibiotic treatment duration compared to a longer duration in adult patients with VAP	Difference in the proportion of participants with the composite endpoint of death and VAP recurrence rate within 60(± 5) days of enrolment	All outcome measures will be assessed within day 60(± 5) of enrolment
Secondary Objectives To define other clinical benefits of shorter antibiotic treatment duration compared to a longer duration in adult patients with VAP	Ventilator-associated events, duration of mechanical ventilation, duration of hospitalisation, acquisition of multidrug resistant infection or colonisation during the hospitalisation, number of days of exposure to antibiotics during hospitalisation, number and types of extrapulmonary infections during hospitalisation (determined from cultures taken from sterile sites), difference in the proportion of participants with primary outcome in subgroups of patients with VAP caused by Gram-negative non-fermenters and carbapenem-resistant bacilli	All outcome measures will be assessed within day 60(± 5) of enrolment
To study the impact of various antibiotic regimen on the microbial community dynamics and diversity in the respiratory and intestinal tracts in individual patients in order to understand colonisation and transmission of MDROs, identify potentially protective components of the microbiome against MDROs	Characteristics of the microbiota will be determined by comparing alpha and beta diversity metrics between the groups of patients, alterations in the repertoire of antibiotic resistant genes, shifts in microbiota functional and metabolic capacity	Respiratory and stool samples will be collected from the study participants within 24 hours of enrolment, weekly during hospitalisation, and at day 28 (± 5) and 60(± 5) after enrolment

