This is a non-inferiority trial with a hierarchical noninferiority–superiority hypothesis. The first analysis to be conducted will be for determination of non-inferiority. Only if non-inferiority is established by this primary analysis, a second analysis for superiority will be conducted using closed testing methods without requiring adjustment of the significance level for multiple comparisons. [39] The trial estimates for the primary outcome will be calculated with the absolute risk difference (proportion of participants with the primary outcome in the short arm minus that in the long arm). Hence, non-inferiority will be concluded if the upper boundaries of the one-sided 95% confidence intervals from both unadjusted and adjusted analyses are below the non-inferiority margin. The purpose of using both adjusted analyses on the intention-to-treat and per-protocol populations to determine non-inferiority is to minimise the inflation of type 1 error associated with non-adherence in non-inferiority trials. [40] Superiority will be declared if the entire confidence intervals for all the trial estimates are above zero.

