10.3. Interim analyses

Four interim analyses will be performed on the primary endpoint whenever 25% of patients has been randomised and have completed the 60 (± 5) days follow-up. The interim analyses will be performed by a trial statistician in coordination with the study team. The statistician will report to the independent data and Data and Safety Monitoring Committee (DSMC). The DSMC will have unblinded access to all data and will discuss the results of the interim-analysis during a DSMC meeting. A trial steering committee will also be constituted and will decide on the continuation of the trial and will report to the central ethics committee. The trial will be terminated if superiority of either short or long treatment durations is shown. We will use the group sequential design adopting the boundaries proposed by Fleming- Harrington- O'Brien ($R=0.8$) [41] to terminate the trial prematurely once the Z value exceeds the defined boundaries for superiority.

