2.6. Hypotheses and Definition of Primary and Secondary Outcomes

Primary end point

The primary end point of the study is the difference in the proportion of participants with the composite endpoint of death and VAP recurrence rate within 60(± 5) days of enrolment.

Death refers to all-cause mortality. VAP recurrences are episodes which satisfy the US CDC VAP criteria, and verified by two independent respiratory or infectious diseases physicians blinded to the randomisation arm.

The first statistical test for the primary end point will be for non-inferiority. Here, the null hypothesis (H_0): $\theta \geq \delta$ will be tested against the alternative (H_1): $\theta < \delta$, where θ is the treatment effect difference between the proportion of participants who have the primary outcome in the short and long treatment strategy groups, and δ is the fixed non-inferiority margin of 12%.

In the event that short is non-inferior to the long treatment strategy, standard two-sided superiority testing will be performed. That is, the null hypothesis (H_0): $\theta = 0$ will be tested against the alternative (H_1): $\theta > 0$, where θ is the treatment effect difference between the proportion of participants who have the primary outcome in the short and long treatment strategy groups.

Secondary end points

All statistical tests for the secondary endpoints are standard two-sided superiority tests.

a) Ventilator-associated events

Definition: Events which satisfy the US CDC VAP criteria ¹ but were not verified by two independent respiratory or infectious diseases physicians.

H_0 : There is no difference in the proportion of participants who have ventilator-associated events in the short and long treatment strategy groups, i.e. $\theta^{VAE} = 0$;

H_1 : There is a difference in the proportion of participants who have ventilator-associated events in the short and long treatment strategy groups, i.e. $\theta^{VAE} \neq 0$;

where θ^{VAE} is the treatment effect difference between the proportion of participants in the short and long treatment strategy groups.

b) Duration of mechanical ventilation

Definition: Total duration of mechanical ventilation during the 60 days of follow-up after enrolment.

H_0 : There is no difference in the total duration of mechanical ventilation in the short and long treatment strategy groups, i.e. $t^v_s = t^v_l$;

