7.2. Statistical Methods Used for Analysis of Primary Outcome

Based on both the ITT and PP population, the proportions of participants experiencing the primary endpoint will be tabulated by treatment group. If the absolute, upper two-sided 90% CIs around the absolute unadjusted difference is less than 12%, then the criteria of non-inferiority will be met.

A multivariable logistic regression model, will be applied on the ITT population to calculate the estimates of the treatment differences adjusted for baseline patient characteristics described above. Categories with low counts may be combined. For example, in the event of comorbidities with very low counts, these comorbidities may be combined to avoid difficulties with the maximum likelihood estimation of the logistic model. Where no

information has been entered on the comorbidities, the participants will be considered not to suffer from these comorbidities.

For the PP population, inverse probability weighting⁹ will be applied to calculate the estimates of the treatment differences using the same baseline patient characteristics as above.

For these multivariate logistic regression models, residual and predicted values produced from the model will be examined to assess the assumptions of the model. Specifically, the assumption of linearity between the predicted log odds and the covariates is assessed by plotting lowess graphs. The independence of the error terms will be considered. Influential cases are investigated by plotting the standardised Pearson's residuals against the predicted probabilities and the leverage of the individual observations.

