7.3. Adjustment of P values for Multiple Testing

There is no multiple testing as only a single primary outcome is considered. All additional analyses are undertaken with an intention to further inform the results from the primary analysis. Therefore significance levels used will be 0.05 and 95% confidence intervals will be reported.

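### The final superiority rule points the wrong way: the estimate is short minus long for death or VAP recurrence, so intervals above zero mean the short arm is worse

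*Protocol*

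**What the plan says.** Protocol section 4 gives the primary objective as "To demonstrate clinical non-inferiority, followed by superiority, of a shorter antibiotic treatment duration". The outcome is a composite of death and VAP recurrence, so fewer events is better.

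Protocol 10.1 defines the estimate as an absolute risk difference: "proportion of participants with the primary outcome in the short arm minus that in the long arm". Non-inferiority is concluded when the upper bounds lie below the margin. If that succeeds, superiority is tested, and the rule is: "Superiority will be declared if the entire confidence intervals for all the trial estimates are above zero". The sentence states no interval level.

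SAP 2.6 sets the non-inferiority null as θ ≥ δ with δ = 12%, which fixes θ as short minus long. It continues: "In the event that short is non-inferior to the long treatment strategy, standard two-sided superiority testing will be performed". The hypotheses that follow are θ = 0 against θ > 0. For the secondary endpoints the same section says "All statistical tests for the secondary endpoints are standard two-sided superiority tests" and prints their alternatives with a not-equal sign.

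SAP 7.2 gives only the non-inferiority criterion, that the "upper two-sided 90% CIs around the absolute unadjusted difference is less than 12" per cent. SAP 7.3 adds: "Therefore significance levels used will be 0.05 and 95% confidence intervals will be reported".

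Protocol 10.3 (Interim analyses) and SAP section 4 have a separate rule based on Z boundaries: "The trial will be terminated if superiority of either short or long treatment durations is shown".

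**The concern.** One paragraph of Protocol 10.1 uses the same scale in two opposite directions. The non-inferiority rule treats large positive differences as bad for the short arm, which is right. The superiority rule treats positive differences as good for it, which is wrong.

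The sentence cannot be rescued by reading it as superiority of the long arm. The test opens only after short has been shown non-inferior, and the objective names superiority of the shorter duration.

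Two errors could follow. A short arm that is truly better could not be declared superior under the protocol's rule. In principle, a short arm that is worse but within the margin could be labelled superior. The check below shows which of these is realistic.

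**Working it through.** **Planned size.** Protocol 10.2 (The Number of Participants) gives 55% events, a 12-point margin, one-sided 5% and 80% power, with a maximum of 412 patients, enrolled as 460. Allocation is 1:1 (Protocol 7.4). The fixed-design formula is n per arm = 2p(1−p)(1.645 + 0.842)²/0.12².

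- At p = 0.55 this gives 212.5, so 213 per arm and 426 in total. At p = 0.60 it gives 414 in total.
- Power with 206 per arm at 55% is 78.9%, and 412/0.9 = 458. The plan's figures are therefore approximately reproduced.

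I use 206 and 230 per arm. The intention-to-treat analysis should be close to 230, because SAP 7.1 counts incomplete follow-up without an event as no event.

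**Direction, from the text alone.** Take 99/230 = 43.0% on short and 127/230 = 55.2% on long.

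- Difference = −12.2 points.
- SE = √(0.430×0.570/230 + 0.552×0.448/230) = 0.0463.
- 95% CI −21.2 to −3.1, Z = −2.63.

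Short is clearly better, yet the interval is not above zero, so the written rule does not call it superior.

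**Can the two written rules hold together at 55%?** With unpooled Wald intervals and equal rates, SE = √(2×0.55×0.45/n). Non-inferiority needs d < 12 − 1.645×SE. The written superiority rule needs d > z×SE. The protocol gives no level for the superiority interval, so I show both 90% and 95%.

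| n per arm | SE | Non-inferior if d below | Written rule met if d above (90% CI) | Written rule met if d above (95% CI) |
|---|---|---|---|---|
| 206 | 0.0490 | +3.9 | +8.1 | +9.6 |
| 230 | 0.0464 | +4.4 | +7.6 | +9.1 |

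The regions do not overlap. At a 60% event rate the 90% figures are nearly the same: below +4.1 or +4.5, against above +7.9 or +7.5.

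**In counts, with 127/230 long-arm events.** Non-inferiority holds up to 137 short-arm events. The written superiority rule starts at 145 (90% CI) or 148 (95% CI). A correctly directed 95% rule is met at 106 or fewer.

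**When could a worse short arm pass both rules?** The limits just meet when (z_upper + z_lower)×√(2p(1−p)/n) = 0.12.

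- With 90% limits on both sides, p is 16.4% or 83.6% (n = 206) and 18.9% or 81.1% (n = 230).
- With a 90% upper and a 95% lower limit, p is 13.1% or 86.9% and 15.0% or 85.0%.
- Going through every pair of counts at both sizes, no result with an average event rate of 20–80% meets both rules.
- A result that does meet both is 195/230 against 181/230: +6.1 points, 90% CI +0.2 to +11.99.

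**What the corrected rule would give.** With the rule turned round (95% interval wholly below zero) and a long-arm rate of 55%, the chance of declaring short superior when it truly lowers the rate by 10 points is 53.2% at 206 per arm and 57.8% at 230. At no true difference it is 2.5%. Under the written rule the chance for the same 10-point benefit is about 0%.

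**The case against.** The strongest reply is that the damage is limited and the intent is easy to guess. Superiority is a conditional second step, and the non-inferiority test, the sample size and the main conclusion do not depend on it. Protocol 10.1 states its sign convention, so a careful analyst would notice the slip. SAP section 1 says primary reporting should follow the SAP, whose test is described as two-sided at 0.05. Such a test would reject for 99 against 127 (|Z| = 2.63 against 1.96). The θ > 0 in SAP 2.6 might also be a garbled symbol. Not-equal signs nearby make that unlikely but do not exclude it.

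Some of this stands. The SAP contradicts itself rather than simply repeating the protocol's rule, so the statement that a better short arm can never be recognised applies to the protocol sentence. The mislabelled-harm case is peripheral. It needs extreme event rates, while the trial excludes SOFA scores above 11 and randomises only after stability criteria are met. It also needs two-sided intervals. The only intervals Protocol 10.1 names are one-sided 95% with an upper bound, and on that reading they could never lie above zero at any event rate.

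It does not remove the problem. The protocol sentence is in plain words and reverses the sign. The SAP's printed alternative points the same wrong way, and SAP 7.2 supplies no rule. SAP section 1 requires deviations to be described and justified, and SAP 9.2 says the statistician is not blinded to allocation. A correct claim of superiority would therefore be a departure from the written rule, made with allocation known. The interim Z rule covers either direction but gives no sign convention and no link to the final interval.

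**Conclusion.** Wrong as written, with high confidence. The sign error follows from Protocol 10.1 alone, and the SAP does not correct it. At the planned 55% event rate the protocol's superiority rule cannot be met once non-inferiority is shown, so the realistic loss is a missed claim of benefit on the second step of the primary objective. Labelling a worse short arm superior would need a common event rate below about 13–19% or above about 81–87%, depending on interval level and sample size. The non-inferiority conclusion and the sample size are not threatened.

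The figures assume unpooled Wald intervals, equal arms and the unadjusted intention-to-treat estimate. Requiring every estimate to agree can only narrow the zones in which both rules hold.

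The documents print no boundary values. Assuming four equal looks at two-sided 5%, the last-look critical Z is about 2.02 (O'Brien-Fleming shape) to 2.36 (constant boundary). Neither is the named Fleming-Harrington-O'Brien design with R = 0.8, but the example at |Z| = 2.63 exceeds both.

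**What to change.** - **Protocol 10.1:** replace the superiority sentence with, for example, *The short arm is declared superior only if, for every trial estimate (short minus long), the whole two-sided 95% interval is below zero.* This keeps the requirement that all estimates agree. The two-sided 95% level is the one that SAP 2.6 and 7.3 point to.
- **SAP 2.6:** define θ explicitly as short minus long, write the superiority alternative as θ ≠ 0, and conclude superiority of short only when the intervals lie below zero.
- **SAP 7.2:** repeat that rule next to the non-inferiority criterion.
- **Both documents:** use one interval level for superiority, and add a sentence saying how it relates to the group-sequential boundary. Four looks at 25% steps may put the last look at the full data.

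The cost is one word, a named arm and a stated level in the protocol; one symbol, one definition and one repeated rule in the SAP; and one linking sentence. It needs no patients, no new data and no change to the sample size.

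### Protocol 10.1 gives no level for the superiority intervals and makes every estimate decide, while the SAP tests at two-sided 5% and names no deciding estimate

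*Protocol*

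**What the plan says.** Protocol 10.1 defines the effect as the absolute risk difference, "proportion of participants with the primary outcome in the short arm minus that in the long arm". Non-inferiority needs the "upper boundaries of the one-sided 95% confidence intervals from both unadjusted and adjusted analyses are below the non-inferiority margin". Superiority is tested next, "without requiring adjustment of the significance level for multiple comparisons", and the rule is that "the entire confidence intervals for all the trial estimates" must lie above zero. No level or sidedness is attached to those intervals. The same section analyses the primary outcome unadjusted and adjusted, in both the per-protocol and the ITT population, so there are four estimates.

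The SAP is more specific on the level and less so on the estimate. Section 2.6: "In the event that short is non-inferior to the long treatment strategy, standard two-sided superiority testing will be performed". Section 7.3: "Therefore significance levels used will be 0.05 and 95% confidence intervals will be reported". Section 7.2 gives a decision criterion for non-inferiority only (upper limit of a two-sided 90% interval under 12 points). No section says which population or estimate decides superiority.

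**The concern.** Closed testing allows the superiority step to reuse the non-inferiority level. With nothing else stated, a reader of the protocol could carry one-sided 5% forward, while a reader of the SAP would use one-sided 2.5% in favour of the short course. A reader of the protocol would also need all four estimates to agree, and a reader of the SAP cannot tell which one counts. The same data could then support a superiority claim under one reading and not under another, with the choice open after the results are known.

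The second issue is the role of the per-protocol set. Protocol 10.1 justifies using both populations by the effect of non-adherence on a non-inferiority conclusion. It gives no reason for extending this to superiority, where ITT already answers the question by a randomised comparison.

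**Working it through.** **1. The rules side by side**

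| | Protocol 10.1 | SAP 2.6, 7.2, 7.3 |
|---|---|---|
| Non-inferiority interval | one-sided 95% upper bound | upper limit of two-sided 90% |
| Level, non-inferiority | one-sided 5% | one-sided 5% |
| Sidedness, superiority | not stated | two-sided |
| Level, superiority | not stated | 0.05 |
| Deciding estimates | all four | not named |

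The documents agree on the level for non-inferiority. The gap is in the superiority step.

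**2. The plan's own figure.** Inputs from the protocol's section on the number of participants: 55% events, 12-point margin, one-sided 5%, 80% power, maximum 412, enrol 460.
- With 55% in both arms: 2 × 0.55 × 0.45 × (1.645 + 0.842)² / 0.12² = 212.5, so 213 per arm and 426 in total, 3.4% above 412.
- With the variance taken at 55% and 67%: 404. A one-sided two-proportion formula for 55% v 67%: 408.
- Power at 412 with 55% in both arms: 78.9%.
- One-sided 2.5% would need 540, so the design level is one-sided 5%.
- 412 / 0.90 = 458, close to 460.

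**3. One interval, one look.** SE = √(2 × 0.55 × 0.45 / n per arm). Benefit of the short course is taken as a negative difference.

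| n per arm | SE | −1.645 × SE | −1.960 × SE |
|---|---|---|---|
| 230 (all randomised) | 4.64 points | −7.6 | −9.1 |
| 206 (412 in total) | 4.90 points | −8.1 | −9.6 |

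ITT is all randomised participants, and SAP 7.1 counts those lost without an event as non-events, so 230 per arm is the relevant planned size. An observed −8.5 points would have an upper limit of −8.5 + 7.6 = −0.9 at one-sided 95%, and −8.5 + 9.1 = +0.6 at two-sided 95%. The false-positive rate in favour of short is 5.0% v 2.5%. If the true difference is −8 points, the chance of passing is 53% v 41% at 230 per arm (49% v 37% at 206).

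**4. All four estimates must pass.** Four correlated normal statistics were simulated under no difference (2 million draws per setting). The correlation between ITT and per-protocol is √(fraction kept), and between unadjusted and adjusted √(1 − R²). The fraction kept (70–100%) and R² (0–30%) are assumptions, because the documents give neither. The per-protocol comparison is treated as unbiased.

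| Per-protocol kept | R² | All four at one-sided 5% | All four at one-sided 2.5% |
|---|---|---|---|
| 100% | 0 | 5.0% | 2.5% |
| 95% | 5% | 3.3% | 1.6% |
| 90% | 10% | 2.7% | 1.2% |
| 80% | 20% | 1.9% | 0.8% |
| 70% | 30% | 1.3% | 0.5% |

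Against 2.5% for one SAP test, the protocol rule at one-sided 5% therefore runs from 2.0 times to about 0.5 times.

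**5. Per-protocol membership.** The protocol's population definitions require 7 days or less of appropriate antibiotics in the short arm and 8 or more in the long arm. Under SAP 2.7, short-arm antibiotics should stop on the day of randomisation, so short-arm membership is largely settled then. Long-arm membership depends on what follows. As defined, a long-arm patient who dies before 8 days of antibiotics cannot be in the set, whereas a short-arm patient who dies after stopping stays in, and death is part of the endpoint. In the other direction, short-arm patients kept on antibiotics beyond day 7 for treatment failure drop out. The net bias could go either way.

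**The case against.** A reader might infer that the protocol tests superiority on the one-sided 95% intervals, so that the level simply doubles or halves with the document followed. The documents do not support that. The one-sided wording is attached to non-inferiority only. An interval with just an upper bound can never lie wholly above zero, so the written rule cannot be applied to such intervals. The protocol shows an omission, not a stated 10% two-sided test. The doubling also ignores the all-estimates requirement, which makes a factor of two the maximum.

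It can also be argued that the SAP closes the gap: its introduction says primary reporting should follow it, and a detailed plan completing a silent protocol sentence is normal practice. This largely stands for the level. It does not settle the deciding estimate, on which the SAP is silent, and it leaves the protocol's all-estimates rule in force.

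The per-protocol requirement can be defended as conservative, since agreement across populations cannot raise the false-positive rate above that of the ITT test alone. That is correct. SAP 7.7 also counts both populations as part of the primary analysis, and SAP 7.2 weights the per-protocol estimate. But weighting on baseline characteristics does not remove selection by deaths or treatment failures after randomisation, so a valid ITT superiority result could be overturned by a biased comparison.

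Finally, the thresholds above are for a single look, whereas both documents set group-sequential boundaries for superiority. That also stands: the thresholds show the size of the gap, not the operating limits of the trial.

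**Conclusion.** The point holds as a gap in a stated decision rule. The protocol leaves the superiority level open and makes four estimates decide. The SAP fixes two-sided 5% and leaves the deciding estimate open.

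If one-sided 5% is carried over, a single interval has up to twice the SAP's false-positive rate, and single-look ITT results between about −7.6 and −9.1 points would be read differently. With all four estimates required, the protocol rule may be looser or stricter than one SAP test. These figures rest on 55% events, 230 per arm, no allowance for interim looks, and assumed per-protocol retention and covariate strength.

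They also take benefit as a negative difference. Read literally, both documents place superiority above zero for an adverse outcome measured as short minus long. That is a separate fault, but the same sentences need correcting. The agreed level for non-inferiority is not affected.

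**What to change.** Put the same sentence in Protocol 10.1 and in SAP 2.6 and 7.2:

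> Superiority of the short course is assessed on the [unadjusted or adjusted: choose one] ITT risk difference (short minus long) and is declared if the upper limit of its two-sided 95% confidence interval is below zero, at a level consistent with the interim boundaries. Per-protocol and all other estimates are supportive.

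Keep the one-sided 95% (two-sided 90%) interval for non-inferiority only.

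The cost is wording, with no change to sample size or data collection. There are two trade-offs. If the protocol was meant at one-sided 5%, the level becomes stricter (at 206 per arm and a true 10-point benefit, the chance of passing on one estimate falls from 65% to 53%). Dropping the all-estimates requirement also gives up a conservative safeguard, which is why the other three estimates should still be reported beside the deciding one.
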